12.5.2 Safety endpoints

All safety evaluations will be performed on the Safety set.

Adverse events

Treatment emergent AEs (events started after the first dose of study treatment and within 84 days after last dose, or events present prior to the first dose of study treatment but increased in severity based on preferred term within 84 days after last dose) will be summarized. Only primary paths within MedDRA will be considered for AE reporting.

AEs will be summarized by presenting, for each treatment group, the number and percentage of subjects having any AE, having an AE in each primary system organ class and having each individual AE (preferred term). Summaries will also be presented for AEs by severity and for study treatment related AEs. If a subject reported more than one AE with the same preferred term, the AE with the greatest severity will be presented. If a subject reported more than one AE within the same primary system organ class, the subject will be counted only once with the greatest severity at the system organ class level, where applicable.

Confidence intervals for relative frequencies will be derived as well according to the score method including continuity correction by Newcombe ([Newcombe 1998](#)).

Separate summaries will be provided for death, SAE, other significant AEs leading to discontinuation and AEs leading to study treatment discontinuation.

A graphical display of relative frequencies within system organ classes will be presented.

Vital signs

Analysis of the vital sign measurements using summary statistics for the change from baseline for each post-baseline visit will be performed. These descriptive summaries will be presented by vital sign and treatment group. Change from baseline will only be summarized for subjects with both baseline and post-baseline values.

Clinical laboratory evaluations

The summary of laboratory evaluations will be presented for two groups of laboratory tests (hematology and serum chemistry). Descriptive summary statistics for the change from baseline to each study visit will be presented. These descriptive summaries will be presented by test group, laboratory test and treatment group. Change from baseline will only be summarized for subjects with both baseline and post baseline.

For each parameter, the maximum change from baseline within each study treatment period will be analyzed analogously.

In addition, shift tables will be provided for all parameters based on Common Toxicity grade Criteria (CTC). For these shift tables, the normal laboratory ranges will be used to evaluate whether a particular laboratory test value was normal, low, or high relative to the baseline value. These summaries will be presented by laboratory test and treatment group. Shifts will be presented for most extreme values post-baseline.

Immunogenicity

All immunogenicity results will be listed by treatment group, subject and visit/time.

Resource utilization

Data relating to resource utilization will be used for the purpose of economic evaluation and will be carried out and reported as a separate activity.

12.5.3 Pharmacokinetics

PK concentrations will be listed by treatment and subject and Cmin will be determined. Descriptive summary statistics will include mean (arithmetic and geometric), SD, and CV (arithmetic and geometric), median, minimum and maximum.

12.5.4 DNA

Exploratory DNA studies are designed to investigate the association between genetic factors (genotypes) and clinical assessments (phenotypes) which are collected during the clinical trial. Without prior evidence of a strong association, a number of possible associations are evaluated with exploratory analyses. A range of statistical tests are used for the analyses. Additional data, from other clinical trials, are often needed to confirm associations. Alternatively, if the number of subjects enrolled in the study is too small to complete proper statistical analyses, the data may be combined, as appropriate, with those from other studies to enlarge the dataset for analysis.

12.5.5 Biomarkers

All biomarker data will be listed by treatment group, subject and visit. Summary statistics will be provided by treatment and visit. The number of values outside of the limits of quantification will be reported in each table.

Exploratory biomarker assessments will be reported separately.

12.5.6 PK/PD relationships

The effect of the secukinumab serum concentration on HiSCR and other endpoints will be investigated if appropriate. Clinically important subject covariates, such as Hurley stage, geographical region, use of antibiotic, baseline body weight, age and baseline AN count will be investigated.

12.5.7 Patient reported outcomes

Please refer to [Section 12.6](#) for the analysis method of Patient reported outcomes.

12.6 Analysis of exploratory endpoints

For the exploratory endpoints analyses, the estimates of the differences between secukinumab groups versus placebo group and the corresponding p-values for pairwise comparisons will not be adjusted for multiple comparisons as no formal confirmatory hypothesis tests are planned.

Subpopulation Analysis

The number and percentage of HiSCR responders in bio-naive patients will be presented by visit up to end of study for each treatment group.

The number and percentage of HiSCR responders in patients with body weight lower and higher than 90kg (<90kg and \geq 90kg) will be presented by visit up to the end of study for each treatment group.

To allow for a pairwise comparison between the two secukinumab regimens and placebo at Week 16 in bio-naive patients, HiSCR at Week 16 will also be analyzed in bio-naive patients using logistic regression with treatment group, geographical region, Hurley stage, baseline AN count use of antibiotic, and baseline body weight as explanatory variables. Odds ratios will be computed for the comparison of secukinumab dose regimens versus placebo utilizing the logistic regression model fitted. In case of response rates of 0% or of 100% in one of the treatment groups, Fisher's exact test will be applied. Risk difference and confidence intervals for risk difference will be provided.

The subgroup analysis of patients with bodyweight lower and higher than 90 kg (<90kg and \geq 90kg) will be analyzed analogously to bio-naive patients.

Modified Hidradenitis Suppurativa Score

Summary statistics will be provided for absolute and percent change from baseline of modified Hidradenitis Suppurativa Score by visit up to end of study.

To allow for a pairwise comparison between two secukinumab regimens and placebo until Week 16, modified Hidradenitis Suppurativa Score up to Week 16 will also be analyzed using a MMRM with treatment group, the respective baseline value, Hurley stage, use of antibiotic, geographical region, baseline bodyweight, visit, baseline mHSS*visit interaction, and treatment group*visit as covariates, with unstructured covariance matrix.

HS-Physician's Global Assessment

HS-PGA responder will be analyzed using logistic regression with treatment group, Hurley stage, geographical region, use of antibiotic, baseline bodyweight, baseline HS-PGA as explanatory variables. Odds ratios will be computed for comparisons of secukinumab dose regimens versus placebo utilizing the logistic regression model fitted. In case of response rates of 0% or of 100% in one of the treatment groups, Fisher's exact test will be applied. Risk difference and confidence intervals for risk difference will be provided. Multiple imputation will be applied in case of missing data and detail information will be specified in Statistical Analysis Plan.

Dermatology Life Quality Index (DLQI)

The Dermatology Life Quality Index (DLQI) is a 10-item dermatology-specific HRQoL measure presented to each subject from the randomization up to the study end. The instrument contains six functional scales (i.e. symptoms and feeling, daily activities, leisure, work and school, personal relationships, treatment). Each question is answered with the following response: "not at all," "a little," "a lot," or "very much". Seven scores will be derived from the DLQI: the total score of each of the six dimensions as well as the total score over all items. The higher the score, the more quality of life is impaired. The DLQI total score will be calculated by summing the score of each question resulting in a maximum of 30 and a minimum of 0.

- DLQI responder: Decrease of ≥ 5.0 points on DLQI total score will be considered as responder and logistic regression will be utilized for analysis with treatment group, Hurley stage, geographical region, use of antibiotic, baseline bodyweight, baseline DLQI score as explanatory variables. Odds ratios and will be computed for comparisons of secukinumab dose regimens versus placebo utilizing the logistic regression model fitted. In case of response rates of 0% or of 100% in one of the treatment groups, Fisher's exact test will be applied. Risk difference and confidence intervals for risk difference will be provided. Multiple imputation will be applied in case of missing data and detail information will be specified in Statistical Analysis Plan.
- Summary statistics will be provided for absolute and percentage change from baseline of the total score of each of the six dimensions as well as the total score by visit up to the end of study for each treatment group.
- To allow for a pairwise comparison between two secukinumab regimens and placebo until Week 16, DLQI score up to Week 16 will also be analyzed using a MMRM with treatment group, the respective baseline value, Hurley stage, use of antibiotic, geographical region, baseline bodyweight, visit, baseline DLQI*visit interaction, and treatment group*visit as covariates, with unstructured covariance matrix.

Work Productivity and Activity Impairment (WPAI)

Summary statistics will be provided for absolute and percentage change from baseline of WPAI component scores by visit up to end of study.

EQ-5D-3L

The EQ-5D is a questionnaire with 5 questions (regarding mobility, self-care, usual activities, pain/discomfort, and anxiety/depression) each with three categories (no problem, moderate problem, severe problems) and a health state assessment from 0 (worst possible health state) to 100 (best possible health state). The number and percentage of subjects in each of the three categories for each question will be presented by visit up to the end of study for each treatment group. Summary statistics will be shown for the health state assessment by visit up to the end of study for each treatment group.

PGI (PGI-s and PGI-c)

The number and percentage of subjects in each category will be presented by visit up to the end of study for each treatment group.

HS Symptom Diary

Summary statistics will be provided for absolute and percentage change from baseline of HS symptom component scores and the absolute HS symptom component score by visit up to end of study.

Inflammatory markers with respect to CRP and ESR

Summary statistics will be provided for absolute and percentage change from baseline of CRP and ESR by visit up to end of study.

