This change has been deemed necessary following the recently available results from study CAIN457A2324, conducted in patients affected by moderate to severe plaque psoriasis and body weight $\geq 90\text{kg}$ and treated with secukinumab 300 mg every four weeks (q4w) or every two weeks (q2w). The study CAIN457A2324 showed that in psoriasis patients who weigh $\geq 90\text{kg}$, secukinumab 300 mg q2w demonstrates a better treatment effect, without altering the well characterized safety profile of secukinumab. Patients with Hidradenitis Suppurativa (HS) are generally heavier than patients with psoriasis ([Storer et al 2018](#)), and it seems reasonable to assume that the same weight-based response seen in psoriasis could apply to HS patients as well. These new findings, paired with the absence of safety concerns noted by the HS Data Monitoring Committee (DMC) when evaluating the 300 mg q2w data from the CAIN457M2301 and CAIN457M2302 studies (17-Jun-2020), and the safety profile seen in study CAIN457A2324, support the revision of the statistical analysis section.

In addition, this amendment introduces the value of the individual lesion count assessed at the baseline visit only to be used as 'baseline' in the statistical analyses, instead of the weighted average across the two screening visits and the baseline (randomization) visit. This change follows the guidance from the FDA advice letter on studies CAIN457M2301 and CAIN457M2302 dated 20-Aug-2019 stating: "As the treatment will be initiated at baseline and not at screening visits, for interpretation of study findings, we recommend that you use the assessments collected at the time of the baseline visit" and also guidance from the FDA advice letter on studies CAIN457M2301/M2302 dated 10-Nov-2020 "For interpretation of study findings, we maintain our recommendation that you use the assessments collected at the randomization visit as the baseline value". The weighted average value will still be considered in sensitivity analyses.

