In order to take into account the variability and the subjectivity of the Hidradenitis Suppurativa Clinical Response (HiSCR), the inter-rater variability when evaluating the draining fistulae and their longevity often requiring surgical excision ([Revuz J 2009](#)), a secondary endpoint evaluating **only** the abscesses and inflammatory nodules (AN) count has been added. Analyzing AN count on the original, continuous scale, enables a more sensitive and granular approach to summarizing the clinical effect of treatment ([Kimball et al 2018](#)).

Moreover, based on the evidence that biologic-naïve (bio-naïve) patients respond better to biologic therapies, including secukinumab, compared to those who are bio-experienced ([Garcia-Montoya and Marzo-Ortega 2018](#)), and considering that it is plausible to assume a dose-response influenced by weight, the exploratory objective section has been updated to include a specific analysis to evaluate the benefit of secukinumab in the bio-naïve population and in the patients with body weight above and below 90 kg. Furthermore, an exploratory objective related

to C-reactive protein (CRP) and erythrocyte sedimentation rate (ESR) has been added to explore treatment effect with regard to inflammatory markers.

Lastly, as introduced in the previous Amendment 01, the number of patients to be randomized has been formally increased to account for the disruptive impact of the COVID-19 pandemic.

Changes to specific sections of the protocol are shown in the track changes version of the protocol using strike through red font for deletions and red underlined for insertions.

The major changes made to the protocol are listed below.

- [Section 2](#) and [Table 2-1](#) have been updated with the addition of the reduction of AN count as secondary and exploratory endpoints, evaluation of inflammatory markers (ESR and CRP) and of the achievement of HiSCR in bio-naive patients, and in patients with body weight lower and higher than 90 kg (<90 kg and \geq 90 kg) as exploratory subgroup analyses.
- [Section 3](#), [Section 5](#) and [Section 12.8](#) have been updated with the increase of the target population (approximately 541 patients).
- [Section 4.2](#) Rationale for dose/regimen and duration of treatment and [Section 4.5](#) have been updated including the available data from the recent CAIN457A2324 study.
- [Section 12.4.1](#) has been edited with updated baseline definition.

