
• To explore the efficacy of secukinumab compared to placebo with respect to HiSCR response after 16 weeks of treatment and the sustained efficacy over time in bio-naïve patients.• To explore the efficacy of secukinumab compared to placebo with respect to HiSCR response after 16 weeks of treatment and the sustained efficacy over time in patients with body weight lower and higher than 90 kg (<90 kg and ≥90 kg).	
• Achievement of HiSCR at Week 16 and up to Week 52 in bio-naïve patients.• Achievement of HiSCR at Week 16 and up to Week 52 in patients with body weight lower and higher than 90 kg (<90kg and ≥90kg).

3 Study design

This is a multicenter, randomized, double-blind, placebo controlled, parallel group study with two secukinumab dose regimens in approximately 541 patients with moderate to severe HS.

The study consists of: Screening (up to 4 weeks), Treatment Period 1 (16 weeks) and Treatment Period 2 (36 weeks). Subjects who prematurely discontinue the study, or who complete the study and cannot or do not wish to continue in a planned optional extension study, will need to complete a post-treatment Follow-Up period (8 weeks).

Safety, efficacy, biomarker and pharmacokinetic measurements of secukinumab will be assessed.

An outline of the study design is presented in [Figure 3-1](#), and a detailed visit and assessment schedule is provided in [Table 8-1](#).

Screening (Screening to Randomization)

A screening period of up to 4 weeks will be used to assess the subject's eligibility and to washout and/or taper prohibited medication(s). Two screening visits will be performed: Visit 1 (Day -28 to Day -14) and Visit 2 (Day -13 to Day -1). Subjects can be re-screened if the subject screen fails due to a transient medical condition or due to an insufficient prohibited medication washout period. Subjects can be re-screened only once and no study-related re-screening procedure should be performed prior to re-consenting the subject.

Important note:

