12.4.2 Statistical model, hypothesis, and method of analysis

The statistical hypotheses for the primary endpoint being tested is that there is no difference in the proportion of HiSCR at Week 16 in any of the secukinumab regimens versus placebo regimen.

Let p_j denote the proportion of HiSCR at Week 16 for treatment regimens j , $j = 0, 1, 2$ where

- 0 corresponds to placebo regimen,
- 1 corresponds to secukinumab 300 mg q2w s.c.,
- 2 corresponds to secukinumab 300 mg q4w s.c.,

In statistical terms, $H_j: p_j = p_0, H_{A_j}: p_j \neq p_0$ for the j th secukinumab regimen, i.e.

H_1 : secukinumab 300 mg q2w s.c. is not different to placebo regimen with respect to HiSCR after 16 weeks of treatment.

H_2 : secukinumab 300 mg q4w s.c. is not different to placebo regimen with respect to HiSCR after 16 weeks of treatment.

The primary analysis method will be logistic regression with treatment group, geographical region, Hurley stage, use of antibiotic, baseline body weight and baseline AN counts as explanatory variables. Odds ratios will be computed for comparisons of secukinumab dose regimens versus placebo utilizing the logistic regression model fitted. In case of response rates of 0% or of 100% in one of the treatment groups, Fisher's exact test will be applied. Risk difference and confidence intervals for risk difference will be provided.

The detailed testing strategy including the primary endpoint analysis is provided in [Section 12.5](#). Efficacy of two secukinumab regimens compared to placebo with respect to HiSCR after 16 weeks of treatment could be demonstrated if H_1 and/or H_2 is/are rejected and the treatment effect is in favor of secukinumab.

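### Protocol 12.6 motivates the <90 / ≥90 kg analysis by a weight-influenced dose-response, but the supplied documents pre-specify no estimate of whether the treatment effect differs by weight

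*Protocol*

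**What the plan says.** **Reason given.** The Amendment 2 rationale draws on a psoriasis study of q2w and q4w dosing in patients of 90 kg or more and says "it seems reasonable to assume that the same weight-based response seen in psoriasis could apply to HS patients as well". It then states that, "considering that it is plausible to assume a dose-response influenced by weight, the exploratory objective section has been updated" to cover bio-naive patients and the two weight groups. Protocol 4.2 also lists higher body weight first among its reasons for studying q2w.

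**Objective.** Protocol Table 2-1, repeated in SAP Table 1-1, words the exploratory objective as efficacy against placebo on HiSCR at Week 16 "and the sustained efficacy over time in patients with body weight lower and higher than 90 kg".

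**Method.** For the bio-naive subgroup, Protocol 12.6 says "HiSCR at Week 16 will also be analyzed in bio-naive patients using logistic regression with treatment group, geographical region, Hurley stage" and the remaining covariates, all as main effects, with each regimen compared with placebo. The weight groups "will be analyzed analogously to bio-naive patients". Responder percentages by visit are also tabulated. Exploratory p-values "will not be adjusted for multiple comparisons as no formal confirmatory hypothesis tests are planned".

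**Elsewhere.**
- The primary model (Protocol 12.4.2) is "logistic regression with treatment group, geographical region, Hurley stage, use of antibiotic, baseline body weight and baseline AN counts as explanatory variables", so weight enters as a main effect only.
- SAP 2.13 and 5.4.2.2 give a mixed logistic model for HiSCR with no weight term. Its only interaction is visit by treatment. The Week 52 SAP has no method for the weight objective.
- Protocol 12.5.6 lists baseline weight as a covariate for exposure-response work, which SAP 2.8 reports separately.

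**The concern.** The rationale is about effect modification: does the benefit of a regimen, or of q2w relative to q4w, depend on weight? The specified analysis answers a neighbouring question: does each regimen beat placebo within each weight group? It yields two sets of odds ratios and p-values and no pre-specified comparison between them. It also contains no q2w v q4w contrast by weight, although a weight-influenced dose-response is a statement about exactly that contrast.

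The risk is one of interpretation. With a stated prior belief that weight matters, one significant and one non-significant subgroup result could easily be taken as confirmation. Such a pattern is common when the effect is the same in both groups. The opposite error is also open: two significant results do not show that the effects are equal.

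**Working it through.** **Inputs from the documents.** Placebo response 30% and secukinumab 50% (Protocol 12.8.1). Originally 471 patients, with placebo pooled in Period 1, so 471/3 = 157 per arm (12.8, 12.1). Now about 180 per arm (Section 3). Alpha 4% for q2w and 1% for q4w, two-sided (12.8).

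**Assumptions.** The share of patients at 90 kg or more is not given, so I use 30% to 70%; results are the same for 30/70 and 70/30. Subgroup tests are at 5% two-sided. The placebo rate is 30% in both weight groups. All figures are for one regimen v placebo, unadjusted for covariates.

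**Step 1: the plan's own power.** With d = 0.20 and mean rate 0.40,

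power = Φ{[d − z√(2·0.40·0.60/n)] / √[(0.30·0.70 + 0.50·0.50)/n]}.

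The continuity correction n_cc = (n/4)[1 + √(1 + 4/(nd))]² turns 157 into an effective n of about 147. That gives 93.0% at 4% and 82.7% at 1%, matching the stated 93% and 83%. Without the correction the values are 94.5% and 85.6%.

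**Step 2: power within each weight group.** Same formula, no continuity correction, z = 1.96, 180 per arm.
- n = 90: (0.2 − 1.96·0.0730)/0.0715 = 0.795, power 78.7%.
- n = 54: (0.2 − 1.96·0.0943)/0.0923 = 0.165, power 56.5%.
- n = 126: (0.2 − 1.96·0.0617)/0.0604 = 1.308, power 90.5%.

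**Step 3: chance that exactly one group is significant when the effect is identical.** The groups are disjoint, so this is P1(1 − P2) + P2(1 − P1).

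| Per arm | Split | Group powers | Exactly one significant |
|---|---|---|---|
| 180 | 50/50 | 78.7%, 78.7% | 2·0.787·0.213 = 34% |
| 180 | 30/70 | 56.5%, 90.5% | 0.565·0.095 + 0.905·0.435 = 45% |
| 157 | 50/50 | 72.9%, 72.9% | 40% |
| 157 | 30/70 | 50.9%, 86.2% | 49% |

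**Step 4: what an interaction estimate would deliver.** The variance of the log ratio of odds ratios is the sum of 1/[n·p(1 − p)] over the four cells (two arms, two weight groups).
- Precision with 30% v 50% in both groups, 50/50 split: 2/(90·0.21) + 2/(90·0.25) = 0.1947, SE 0.441, exp(1.96·0.441) = 2.37. At 30/70 the SE is 0.481 and the factor is 2.57.
- Power if active response is 60% below and 40% above 90 kg: ratio of odds ratios (0.6/0.4)/(0.4/0.6) = 2.25, log 0.811. At 50/50, SE = √[2/(90·0.21) + 2/(90·0.24)] = 0.445 and Φ(0.811/0.445 − 1.96) is about 44%. At 30/70 the SE is 0.486 and power is about 39%.
- For 55% v 45% (ratio 1.49), power is about 13% to 15%.
- The ratio detectable with 80% power is about 3.4 (50/50) to 3.9 (30/70).

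**The case against.** The best defence is that objective and method agree. Table 2-1 asks about efficacy against placebo in each weight group, and 12.6 delivers that. The amendment sentence itself ends by describing an evaluation of benefit in those groups. This stands: no stated objective goes unanswered, and the mismatch is only with the reason given for adding the analysis.

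A reader might infer that the planned analysis cannot show a difference by weight. That goes too far. The groups are disjoint, so their estimates are independent, and 12.6 provides odds ratios and risk differences with confidence intervals. A ratio of odds ratios could be formed afterwards given standard errors or intervals for the odds ratios. What is missing is a pre-specified contrast, not the information.

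A reader might also infer that the sponsor means to judge weight dependence by comparing subgroup p-values. Neither document says so, and 12.6 disclaims confirmatory testing. The 34% to 45% is the error rate of a reading the plan does not prescribe.

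Two further points stand. An interaction term has little power here, so it will often be inconclusive. And SAP Section 1 refers the primary and secondary analyses to a separate Week 16 SAP, which was not available and may already hold an interaction analysis. The exposure-response work in 12.5.6 bears on the weight rationale but is not a comparison of treatment effects by weight.

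**Conclusion.** The point holds as a low-cost improvement to an exploratory analysis. The weight-influenced dose-response is the sponsor's stated reason for the analysis. The protocol and the Week 52 SAP specify neither an estimate of how the treatment effect differs by weight nor a q2w v q4w contrast by weight. This is established for those two documents only.

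If the separate p-values were used to judge the question, an identical effect would give exactly one significant group in 34% to 45% of trials for one regimen at 180 per arm (40% to 49% at 157). This rests on the protocol's 30% v 50% in both groups, a 5% two-sided level, and an assumed weight split between 50/50 and 30/70.

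The primary and secondary conclusions and the alpha allocation are unaffected.

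**What to change.** In Protocol 12.6, keep the within-group models and add one exploratory logistic model for HiSCR at Week 16 on the FAS. Include treatment, weight stratum, the treatment-by-weight-stratum interaction and the planned covariates, with missing Week 16 data handled as in the within-group models. Report:

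- odds ratios and risk differences against placebo in each weight stratum;
- for each regimen, the ratio of odds ratios between strata with its 95% CI;
- the q2w v q4w contrast in each stratum.

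State that this is estimation and not a powered test: the 95% CI will be about the estimate divided and multiplied by 2.4 to 2.6, with about 39% to 44% power for a ratio of odds ratios of 2.25. State also that significance in one stratum only is not evidence of a difference. If the Week 16 SAP already contains such a model, a cross-reference in 12.6 is enough.

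The cost is one extra model. Weight at 90 kg is already a randomisation stratum (Protocol 6.3.2), so no new data are needed, and no alpha is spent.
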